4.4.2 Treatment compliance

Treatment compliance per subject will be assessed using the ITT Population.

The volume per dose recorded by subjects (mL) in the eDiary, the corresponding dose (IU/kg) per subject, the planned volume per dose per subject (mL), and the planned dose per subject (IU/kg) will be summarized by descriptive statistics.

Treatment compliance per subject based on subject reported volume in the eDiary will be assessed by treatment as follows:

For each dose of a subject the treatment compliance based on volume (%) will be calculated as

$$100 * (\text{volume (mL) of investigational product reported in the eDiary} / \text{planned volume (mL) of investigational drug}).$$

Then the mean of these compliance measures will be calculated per subject. Descriptive statistics will be presented.

A by-subject listing will be produced for all compliance variables.

4.5 Prior and Concomitant Medication

Medications that start and end before the date of the first administration of the corresponding study treatment will be classified as ‘prior’ medication for that study treatment. Medications that start before the date of the first administration of the corresponding study treatment, and end on or after the date of the first corresponding study treatment will be classified as ‘prior / concomitant’ medication for that study treatment. Medications that start on or after the date of the first administration of the corresponding study treatment and before the date of the last visit in the corresponding study treatment will be classified as ‘concomitant’ medication for that study treatment.

All drugs and/or procedures being administered before the time a subject signed informed consent/assent (as appropriate) will be included in the medical history for “CSL830- Naïve” Subjects. Prior medications include all medications taken within 3 months prior to screening day of study CSL830_3002. For “CSL830-Interrupted” Subjects and “CSL830-Continuation” Subjects drugs and/or procedures excluding HAE medications in study CSL830_3001 will be included in the medical history.

If medication start and/or stop dates are missing or partial, medications will be assumed to be ‘concomitant’, unless there is clear evidence (through comparison of partial dates) to suggest that the medication started prior to the date of the first administration of the corresponding study treatment. If there is clear evidence to suggest that the medication started prior to the date of first administration of the corresponding study treatment, the medication will be assumed to be ‘prior / concomitant’, unless there is clear evidence to suggest that the medication stopped prior to the date of the first administration of the corresponding study treatment. If this is the case, the medication will be considered ‘prior’.

Medications which have a start date in the period from the completion visit in Period 2 to the Follow-up Visit or the first visit of the Extension Period will be assigned to Treatment Period 2. Medications which have a start date in the period from the completion visit of the Extension Period to the Follow-up Visit of the Extension Period will be assigned to the Extension Period.

The number and percentage of subjects with medication taken ‘prior / concomitant’ and/or ‘concomitant’ will be presented by ATC class and PT as described in [Section 4.1](#).

Note that a subject will only be counted once regardless of how many times they took medication reported under the same PT.

A by-subject listing will be produced for all ‘prior / concomitant’ and ‘concomitant’ medications.

Notes:

- Medications are coded using World Health Organization (WHO) Drug dictionary version B2 Enhanced March 2013.
- Therapeutic class will be the level 4 anatomical therapeutic chemical (ATC) name unless coding is not available at level 4. In these cases level 3 ATC name will be used. Similarly, if the level 3 ATC name is not available then the level 2 ATC name will be used and if the level 2 ATC name is not available then the level 1 ATC name will be used.

4.6 Efficacy Analysis

The secondary efficacy analyses will be carried out for the ITT and PP Populations. The ITT Population is used as the primary analysis and the Per Protocol Population will be used as secondary analysis.

The evaluation period for efficacy assessments will be from the start (Day 1) of Week 3 of a treatment in Treatment Period 1 until the End of Study Visit (Week 53 Visit) or the last administration of CSL830 + 4 days (whichever occurs first) for subjects who are not participating in the Extension Period. For subjects who are taking part in the Extension Period, the evaluation period will be from the start (Day 1) of Week 3 of the treatment in Treatment Period 1 until the End of Study Visit of the Extension Period (Week 88) or the last administration of CSL830 + 4 days (whichever occurs first). For subjects who are participating in the Extension Period and who have a rest period between Treatment Period 2 and the Extension Period, the evaluation period will exclude the rest period between the Week 53 Visit or the last administration of CSL830 + 4 days (whichever occurs first) of Treatment Period 2 and the first visit of the Extension Period.

CCI

Each day, subjects are to enter HAE symptoms (yes/no) into their eDiary and, if yes, the severity(s) and location(s) of the HAE symptom(s). Investigator-reported HAE attacks are based upon review of patient diaries and review of relevant interim medical history, including hospital/medical records and any information provided by the subject. Using medical judgment, the investigator is to determine the occurrence of an HAE attack and report its start and stop dates (generally from onset of the first symptom preceded by symptom-free day to the last symptom preceding symptom-free day), its severity (based upon maximal intensity of any symptom as judged by the investigator), and its location(s) (all involved locations as judged by the investigator are to be reported). Each HAE attack is to be preceded and followed by an attack-free day. For every visit, the Investigator is to report all HAE attacks that have occurred in the interim since the last visit the subject attended.

For the analyses, a HAE attack is defined on the basis of the HAE attacks reported by the investigator using the HAE attack eCRF and all HAE attacks reported by the investigator will be included in the analyses. The investigator reported HAE attacks that were not preceded and followed by an attack-free day are merged into one HAE attack, with the earliest start

date, the latest end date and the most severe severity of the individual HAE attacks. If the start date of a merged HAE attack is falling in the first two weeks of a treatment period, this merged HAE attack will not be included in the analyses. If the investigator entered the individual HAE attacks during the same time frame but in different attack locations, the corresponding merged HAE attack will be given the HAE attack location of “multiple”.

All secondary and exploratory efficacy endpoints which include HAE attacks will be analysed as described above as the primary analysis approach. In addition, a sensitivity analysis will be performed for all secondary and exploratory efficacy endpoints in which HAE attacks are analyzed as they are reported by the investigator in the attack eCRF. This sensitivity analysis will be regarded as secondary.

A by-subject listing will be produced for all HAE attacks of the primary analysis approach and an additional by-subject listing will be produced for all HAE attacks reported by the investigator in the eCRF.

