4.1.2 Inclusion Criteria

Subjects meeting all of the following inclusion criteria may be enrolled (randomized) into the study:

1. Capable of providing written informed consent/assent (as appropriate) and willing and able to adhere to all protocol requirements, and/or the subject’s parent(s) or legally acceptable representative(s) capable of providing written informed consent.
2. Male or female.
3. Aged 6 years or older at the time of providing written informed consent/assent (as appropriate).
4. A diagnosis of HAE (type I or II), as determined by the following: a clinical history consistent with HAE *and* CCI [REDACTED]
[REDACTED]
 - For “CSL830-Naïve” Subjects: Historically documented CCI [REDACTED]
[REDACTED] that are compatible with participation will be accepted; however, if historical documentation is unavailable, then the tests may be conducted at Screening. Biochemical confirmation of HAE (type I or II) diagnosis must be established for a subject before starting the Treatment Period 1.
 - For “CSL830-Interrupted” Subjects AND “CSL830-Continuation” Subjects: The documentation that was used to confirm eligibility in CSL830_3001 will be used to verify the required value for inclusion in the current study (CSL830_3002).
5. Have experienced HAE attacks (requiring acute treatment, medical attention or causing significant functional impairment) as described below:

- For “CSL830-Naïve” Subjects:
 - “CSL830-Naïve” Subjects using intravenous C1-INH as routine (long-term) prophylaxis against HAE attacks must have experienced 4 HAE attacks over *any* consecutive 2-month period before the initiation of intravenous C1-INH prophylaxis and before the CSL830_3002 Screening Visit, as documented in the subject medical records.
 - All other “CSL830-Naïve” Subjects (eg, treated using oral HAE prophylaxis against HAE attacks or on-demand treatment) must have experienced 4 HAE attacks over a consecutive 2-month period within the 3 months before the CSL830_3002 Screening Visit, as documented in the subject medical records.
 - For “CSL830-Continuation” Subjects AND “CSL830-Interrupted” Subjects:

Subjects must have experienced 4 HAE attacks over a consecutive 2-month period within the 3 months before the CSL830_3001 Screening Visit, as documented in the subject medical records (ie, the HAE attack frequency required for eligibility to participate in study CSL830_3001).

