3.3.5 Subject Assessments with the eDiary

Following randomization, subjects will report the following information in the eDiary:

- Details of the administration of CSL830 (i.e., dose, date, start time of injection, location of injection, and needle type used).
- Local reactions at the site of CSL830 administration (discomfort [e.g., pain, burning], swelling, bruising, itching) (yes/no).
- Prodromal symptoms experienced (fatigue, rash, muscle aches, nausea, tingling) (yes/no).
- HAE symptoms experienced (yes/no).
- Day and time of HAE symptom onset.
- Location of HAE symptom(s) from most severe to least severe (face/lips; tongue/inside mouth; throat/voice box; abdominal; genitourinary; extremities [right arm, left arm, right leg, left leg]).
- Location of primary HAE symptom (face/lips; tongue/inside mouth; throat/voice box; abdominal; genitourinary; extremities [right arm, left arm, right leg, left leg]).
- Severity of HAE symptom(s) (mild, moderate, or severe).
- Medication for the treatment of HAE attacks is needed (yes/no).
- If medication for the treatment of HAE attacks is needed:
 - Medication used (Berinert, Kalbitor, Firazyr, C1-INH other than Berinert, fresh frozen plasma, other).
 - Dose administered.
 - Day and time started.
 - Administration of medication by a health-care professional (yes/no).
- AEs (yes/no).
- Other concomitant medication (yes/no).

CCI

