4.6.3.1 The percentage of subjects who are responders

The percentage reduction in the time-normalized number of HAE attacks per subject is calculated as:

- $100\% * [1 - (\text{the time-normalized number of HAE attacks when treated with CSL830}) / (\text{the time-normalized number of HAE attacks used to qualify for participation in the current study})]$

The HAE attacks used to qualify for participation in the current study are derived from the subject medical records:

- “CSL830-Naïve” Subjects using intravenous C1-INH as routine (long-term) prophylaxis against HAE attacks must have experienced 4 HAE attacks over *any* consecutive 2-month period before the initiation of intravenous C1-INH prophylaxis and before the CSL830_3002 Screening Visit, as documented in the subject medical records.

- All other “CSL830-Naïve” Subjects (e.g., treated using oral HAE prophylaxis against HAE attacks or on-demand treatment) must have experienced 4 HAE attacks over a consecutive 2-month period within the 3 months before the CSL830_3002 Screening Visit, as documented in the subject medical records.
- For “CSL830-Continuation” Subjects and “CSL830-Interrupted” Subjects: Subjects must have experienced 4 HAE attacks over a consecutive 2-month period within the 3 months before the CSL830_3001 Screening Visit, as documented in the subject medical records (i.e., the HAE attack frequency required for eligibility to participate in study CSL830_3001).

A subject is classified as a responder if the percentage reduction is $\geq 50\%$. A subject whose time-normalized number of attacks cannot be calculated in the treatment periods will be excluded from the calculation of the percentage of responder analysis.

The number and percentage of responders and non-responders and the difference in the percentage of responder between the 60IU/kg CSL830 and 40IU/kg CSL830 treatments will be summarized. 95% Wilson Confidence Intervals will be calculated for all percentages.

The analyses will be repeated including only subjects who have no dose increase.

Subgroup analyses will be performed for age (≤ 17 years / >17 years) and subjects' completion status (completed study / discontinued early). The number and percentage of responders and non-responders will also be calculated and presented descriptively for each of the following time windows:

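### In the readable text, the responder ratio sets all investigator-reported on-treatment attacks against a baseline restricted by inclusion criterion 5, so its two sides use different attack definitions

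*SAP*

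**What the plan says.** **On-treatment side.** SAP 4.6 has the investigator identify attacks from the daily diary and the interim history: "Using medical judgment, the investigator is to determine the occurrence of an HAE attack and report its start and stop dates". It then says that "all HAE attacks reported by the investigator will be included in the analyses". The diary in SAP 3.3.5 collects "Severity of HAE symptom(s) (mild, moderate, or severe") and "Medication for the treatment of HAE attacks is needed (yes/no"), so mild and untreated symptoms are among the material that the investigator reviews. Reported attacks without an attack-free day between them are merged into one, which keeps the worst severity.

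**Baseline side.** SAP 4.6.3.1 divides by "the time-normalized number of HAE attacks used to qualify for participation in the current study". On their source it says: "The HAE attacks used to qualify for participation in the current study are derived from the subject medical records". SAP 2.2.2 and 4.6.3 tie these attacks to inclusion criterion 5, which opens: "Have experienced HAE attacks (requiring acute treatment, medical attention or causing significant functional impairment").

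**Planned variants.** The SAP 4.6 sensitivity analysis undoes the merging. SAP 4.6.3.1 repeats the analysis in subjects without a dose increase, by age, by completion status and over several time windows. SAP 4.14 says that analyses of treated attacks were added in Section 4.9.3, which is not readable.

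**The concern.** A percentage reduction means what it says only if the same kind of event is counted before and during treatment. Here a mild attack that was not treated, led to no medical attention and did not significantly impair function can enter the on-treatment count, yet it lies outside the baseline definition. None of the readable variants changes the type of attack counted; they change merging, subjects or time windows.

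At stake is the interpretation of one of the two secondary efficacy endpoints, together with the planned difference in responder percentage between 60 and 40 IU/kg. A subject whose attacks became milder as well as fewer could be scored as a non-responder because of the broader count. The summary in SAP 4.6.3.2 of on-treatment against pre-study attack numbers raises the same question. The classification of fewer than 1 attack per 4 weeks does not, because it uses no baseline. The primary safety endpoints are not affected.

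**Working it through.** The documents give no figure for this comparison, so there is none to reproduce.

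**Inputs**
- A: rate of all investigator-reported on-treatment attacks (SAP 4.6).
- B: qualifying rate (SAP 4.6.3.1; Protocol 4.1.2, criterion 5).
- Cut-off: a reduction of at least 50% (SAP 4.6.3.1).
- q: share of on-treatment attacks below the criterion 5 threshold. It is not in the documents. Values of 10% to 40% are assumed for illustration.

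**Step 1. Effect of the definition alone**

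Planned reduction: P = 1 − A/B.

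Reduction in qualifying-type attacks: L = 1 − (1 − q)A/B.

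At P = 50%, A/B = 0.5, so L = 1 − 0.5(1 − q) = 50% + q/2.

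In the other direction, P = 1 − (1 − L)/(1 − q). For L = 60% this is 1 − 0.4/(1 − q).

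| q (assumed) | L at the planned 50% cut-off | P shown when L = 60% |
|---|---|---|
| 10% | 55% | 55.6% |
| 20% | 60% | 50.0% |
| 30% | 65% | 42.9% |
| 40% | 70% | 33.3% |

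A 60% reduction in qualifying-type attacks becomes non-response once 0.4/(1 − q) exceeds 0.5, that is, once q exceeds 20%. A subject with L of at least 50% + q/2 is a responder either way.

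**Step 2. On the rate scale**

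The minimum baseline is 4 attacks in 2 months. Taking 2 months as 60.875 days, this is 4/60.875 × 28 = 1.84 per 28 days, and the responder limit is 0.92. If only qualifying-type attacks counted, the same subject could have 0.92/(1 − q) attacks of any kind: 1.02 at q = 10%, 1.31 at q = 30%.

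**Step 3. Illustrative effect on the responder percentage**

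A gamma-Poisson simulation assumed 50 weeks of observation, gamma shape 1, a mean qualifying-type rate of 0.5, 0.8 or 1.1 per 28 days, every baseline at the minimum, the same q for all subjects and no merging. The all-attacks responder percentage fell below the qualifying-type percentage by about 3 to 4 points at q = 10% and 11 to 13 points at q = 30%. None of these inputs comes from the documents.

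**Step 4. Merging works the other way**

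Suppose merging removes a share r of reported on-treatment attacks, baseline episodes are unmerged, and q is unaffected. With A now the unmerged rate, P = 1 − (1 − r)A/B while L = 1 − (1 − q)A/B. The two effects cancel at r = q, and the net error favours the drug if r exceeds q. The documents give neither r nor how contiguous episodes were counted in the medical records. The planned unmerged analysis removes r from the on-treatment side but leaves q untouched.

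**The case against.** The strongest objection is that the decisive text may be blacked out. Protocol 3.2 refers to attacks as defined or determined per protocol, but no such definition is readable. Protocol 10.2 is redacted, and a redacted block precedes the ascertainment paragraph in SAP 4.6. The SAP sentence says which reported attacks enter the analysis, not what makes an attack reportable. A hidden definition could narrow or close the gap, and SAP 4.9.3 may already contain a suitable treated-attack analysis. This stands. A reader might infer that the plan has no on-treatment threshold at all or omits the remedy; the documents support neither. What can be said is that no readable text applies criterion 5 on treatment or links 4.9.3 to the responder endpoint.

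A reader might also infer that any mild untreated attack would have been excluded at baseline. That goes too far: medical attention alone satisfies criterion 5.

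A third objection is that the endpoint is defined on the number of attacks, and that counting all reported attacks is defensible in an open-label study, where rescue use and severity grading are decided by people who know the treatment. This stands as a reason to keep the planned analysis. It does not make the baseline comparable.

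Finally, the endpoint is secondary in a safety study, and the definitional effect on its own lowers the responder percentage. That limits the consequence, but a reported 50% reduction would still need its definition stated.

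**Conclusion.** The point holds as a mismatch of attack definitions in the readable text, conditional on the redacted sections not narrowing the on-treatment side. For q between 10% and 40%, the 50% cut-off corresponds to a 55% to 70% reduction in qualifying-type attacks, with q assumed and the definition taken as the only difference in scale.

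Two stronger conclusions are tempting. One is that the planned responder percentage is biased against the drug by a known amount. The documents do not support this: q is not given, merging pushes the other way, and ascertainment from a daily diary rather than medical records is a further difference of unknown size. The net error is therefore unknown. The other is that the comparison of 60 with 40 IU/kg is distorted. That would follow if q differed between doses, but nothing in the documents shows that it does. The supplementary table would make this visible.

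The change is worth making but not critical: it concerns the interpretation of a secondary endpoint.

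**What to change.** 1. Keep the all-attacks responder analysis. State in SAP 4.6.3.1 which attack definition applies to each side of the ratio and, if no narrower rule governs, that the on-treatment definition is broader than the baseline one.
2. Unless SAP 4.9.3 already provides it, add a supplementary responder analysis by dose group, with the 60-versus-40 IU/kg difference. Count only on-treatment attacks that were treated with rescue medication or graded moderate or severe by the investigator. Administration by a health-care professional need not be a separate condition, since SAP 3.3.5 records it only when medication was needed.
3. Label this table an approximation to criterion 5. Severity is a proxy for functional impairment and is graded open-label, and medical attention without drug treatment may be missed.
4. Say whether any merging rule applies to baseline attacks, so that the opposing effect can be judged.

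The cost is a few sentences of SAP text and one table. Investigator-graded severity and rescue use are already collected, and SAP 4.14 already links rescue medication to merged attacks for another analysis. The price is a second responder figure that matches criterion 5 only roughly.

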4.6.3 Secondary efficacy endpoints

Secondary efficacy endpoints are:

- a. The percentage of subjects who are responders. The “response” is defined as a $\geq 50\%$ relative reduction in the time-normalized number of HAE attacks during treatment with CSL830, compared with the time-normalized number of attacks that is used to qualify the subject for participation in this study (see Section 4.1.2 of the protocol [inclusion criterion 5]).
- b. The percentage of subjects who experience a time-normalized number of HAE attacks of < 1 HAE attack per 4-week period.

The time-normalized number of HAE attacks during treatment with CSL830 is calculated per subject as:

- The number of HAE attacks /length of stay of subject (days);

where the length of stay for subjects who are not participating in the Extension Period is calculated as:

- Date of End of Study Visit at Week 53, date of the 4th day post the last IMP administration or study discontinuation date (whichever occurs first) – date of Day 1 Week 3 + 1.

for HAE attacks with start date before (including) the Week 53 visit, the last administration of CSL830 + 4 days or study discontinuation date (whichever occurs first).

For subjects who are continuing into the Extension Period and have no rest period, the length of stay is calculated as:

- Date of End of Study Visit at Week 88, date of the 4th day post the last IMP administration or study discontinuation date (whichever occurs first) – date of Day 1 Week 3 + 1.

for HAE attacks with start date before (including) the Week 88 visit, the last administration of CSL830 + 4 days or study discontinuation date (whichever occurs first).

For subjects who are continuing into the Extension Period and have a rest period, the length of stay is calculated as:

- {Date of End of Study Visit at Week 53, date of the 4th day post the last IMP administration in Treatment Period 2 (whichever occurs first) – date of Day 1 Week 3 + 1} + {Date of End of Study Visit at Week 88, date of the 4th day post the last IMP administration in the Extension Period or study discontinuation date (whichever occurs first) – date of first visit of the Extension Period + 1}.

for HAE attacks with start date outside the rest period and before (including) the Week 88 Visit or the last administration of CSL830 + 4 days or study discontinuation date (whichever occurs first).

HAE attacks with start dates

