- between one day after the End of Study Visit or 4th day post last IMP administration [whichever occurs first] and the Follow-up Visit of Treatment Period 2 (applicable for subjects not participating in the Extension Period)
- between one day after the End of Study Visit or 4th day post last IMP administration [whichever occurs first] and the Extension Follow-up Visit (applicable for subjects participating in the Extension Period)
- between one day after the Week 53 Visit or 4th day post last IMP administration [whichever is first] of Treatment Period 2 and the first visit of the Extension Period (applicable for subjects who are taking part in the Extension Period and who have a rest period)

will not be included in the analyses (ie the numerator “number of HAE attacks”).

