- 1) For all subjects: every 6 months excluding the first 2 weeks in Period 1 (for subject who are participating in the Extension Period and who have a rest period: the rest period will also be excluded),
- 2) For subjects who are not participating in the Extension Period: first 6 months and first 12 months excluding the first 2 weeks in Period 1,
- 3) For subjects who are participating in the Extension Period: first 6 months, first 12 months, first 18 months and first 22 months excluding the first 2 weeks in Period 1 (for subject who have a rest period: the rest period will also be excluded).

Subjects who undergo a dose increase will be flagged in the listing.

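### SAP 4.6 drops early merged attacks in an unnamed treatment period, while the denominator removes only the first two weeks of Treatment Period 1; programmed literally, overall attack rates would be up to about 4% too low

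*SAP*

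**What the plan says.** SAP 4.6 bases the main efficacy analysis on investigator-reported attacks. Attacks not separated by an attack-free day are merged, and the merged attack takes the earliest start date. The same paragraph then sets two rules:

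- As a general rule, "all HAE attacks reported by the investigator will be included in the analyses".
- As an exception, a merged attack is left out "If the start date of a merged HAE attack is falling in the first two weeks of a treatment period". No period is named.

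The remaining text on the time window refers to Treatment Period 1 or counts from its third week:

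- **Evaluation period (SAP 4.6, restated in 4.14):** it runs "from the start (Day 1) of Week 3 of a treatment in Treatment Period 1".
- **Length of stay (SAP 4.6.3):** the count starts at the "date of Day 1 Week 3 + 1" term. After a rest period it restarts with the "date of first visit of the Extension Period + 1" term. Nothing is deducted at the start of Treatment Period 2 or of the Extension.
- **Attacks counted (SAP 4.6.3):** the formula for subjects outside the Extension is "for HAE attacks with start date before (including) the Week 53 visit", last dose plus 4 days, or discontinuation. The listed exclusions concern follow-up and the rest period, for example those "between one day after the Week 53 Visit or 4th day post last IMP administration". None concerns early Treatment Period 2 or early Extension.
- **Time windows (SAP 4.6.3.1):** the first is "every 6 months excluding the first 2 weeks in Period 1".

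Treatment Period 2 starts at the Week 25 Visit (SAP 3.1.3), and SAP 3.3.1 describes the Extension as containing a treatment period of 88 weeks. Both fit the unnamed reference.

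**The concern.** An attack rate is meaningful only if numerator and denominator cover the same days. The sentence in SAP 4.6 is the one that says what happens to a merged attack with an early start, so a programmer building the attack dataset would work from it. Applied to every period, it would discard attacks from the first two weeks of Treatment Period 2 and of the Extension while those days still counted as observed time.

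Both secondary efficacy endpoints use this rate. The endpoint of fewer than one attack per 4 weeks applies a cut-off to it. The responder endpoint divides it by the qualifying rate, which comes from medical records and would not be affected. A rate that is too low therefore improves both results.

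A programmer might find a per-period exclusion plausible, because SAP 3.2 uses two-week dose-stable periods in the later periods. However, SAP 3.2 also says that the dose-increase evaluation period plays no part in the statistical analyses, so it gives no reason to drop those attacks.

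**Working it through.** The plan gives no on-treatment attack rate and no bias figure, so there is none to reproduce. The check is a day count.

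**Inputs (nominal days, protocol schedules of events and SAP 4.6.3).** Start of counting: Day 15. Week 25 Visit: Day 169. Week 53 Visit: Day 367. Final Extension visit: Extension Day 617. Six-month window: 183 days (assumption; the SAP gives no length in days).

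**Formula.** With a constant attack rate, the relative shortfall is the days whose attacks are dropped divided by the days in the denominator.

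| Setting | Denominator (days) | Days losing attacks | Shortfall |
|---|---|---|---|
| No Extension | 367 − 15 + 1 = 353 | 14 | 14/353 = 4.0% |
| Extension, no rest | (366 + 617) − 15 + 1 = 969 | 28 | 28/969 = 2.9% |
| Extension, with rest | 353 + 617 = 970 | 28 | 28/970 = 2.9% |
| First six-month window, Days 15–197 | 183 | 14 (Days 169–182) | 14/183 = 7.7% |

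If only Treatment Period 2 were affected, the Extension figure would be 14/969 = 1.4%. If the exclusion is limited to Treatment Period 1, numerator and denominator both cover Days 15–367 and the shortfall is 0%.

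**Cut-off of 1 attack per 28 days.** The true rate that would be reported as exactly 1 is 1/(1 − shortfall): 1/(1 − 14/353) = 1.04, 1/(1 − 28/969) = 1.03 and 1/(1 − 14/183) = 1.08. For one subject, 13 attacks in 353 days give 13 × 28/353 = 1.03. Dropping one gives 12 × 28/353 = 0.95, which changes the classification.

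**Responder cut-off of 50%.** The true reduction that would be reported as exactly 50% is 1 − 0.5/(1 − shortfall): 47.9% without the Extension, 48.5% with it and 45.9% in the first window.

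**Chance of being classified below 1 per 4 weeks.** Attack counts are taken as Poisson, which is an assumption.

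| True rate per 28 days | 353 days: all counted | 353 days: literal rule | 969 days: all counted | 969 days: literal rule |
|---|---|---|---|---|
| 0.8 | 0.783 | 0.820 | 0.899 | 0.925 |
| 1.0 | 0.507 | 0.564 | 0.504 | 0.572 |
| 1.2 | 0.257 | 0.309 | 0.136 | 0.180 |

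The 353-day columns need care because attacks are whole numbers. If the 14 days also left the denominator, it would be 353 − 14 = 339 days. The limit would still be 12 attacks (339/28 = 12.1; 353/28 = 12.6), and the probabilities would equal the literal-rule column. At exactly that length, the gain is relative to counting every attack and does not separate the literal rule from a matched exclusion. With the Extension, a matched exclusion (969 − 28 = 941 days) lowers the limit from 34 to 33 attacks and gives 0.504 at a true rate of 1.0, so there the mismatch itself produces the gain.

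**The case against.** The strongest reply is that the SAP, read as a whole, means Treatment Period 1. The evaluation period, its restatement in 4.14, the length of stay and the time windows all point there, and the explicit exclusions in 4.6.3 mention neither early Treatment Period 2 nor the early Extension. The sentence may have a narrow purpose: a merged attack takes its earliest start date, so one that begins in the run-in and continues past it falls outside the window. On that reading there is no bias. This stands as evidence of intent, but it also confirms that the sentence disagrees with the rest of the SAP.

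Other points also stand:

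- The figures are upper values. If a merged attack means only one built from several entries, fewer attacks are lost.
- At 1 attack per 28 days, the expected loss over 353 days is 14/28 = 0.5 attacks out of 353/28 = 12.6. The 13-attack example sits at the cut-off.
- The endpoints are secondary and descriptive. There is no primary efficacy analysis, and primary safety does not use this rate. For equal follow-up, the relative shortfall is the same at both doses.

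Two stronger inferences are not supported:

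- A reader might infer that the as-reported sensitivity analysis omits the two-week rule and so would differ from the main analysis for a reason unrelated to merging. The SAP does not say whether the rule applies there. It follows only that this analysis cannot be relied on to reveal the error.
- A reader might place the 7.7% in a window opening at Week 25. The SAP defines no such window. The figure belongs to the first six-month window, which contains the start of Treatment Period 2.

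**Conclusion.** The SAP contradicts itself on which attacks count: the merged-attack sentence in 4.6 is not limited to Treatment Period 1, and the denominator and the other window definitions are. Followed literally, the sentence gives mismatched rates that favour the drug on both secondary efficacy endpoints. The shortfall is up to about 4.0% without the Extension, 2.9% with it, and 7.7% in the first six-month window.

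These sizes assume literal programming, every analysed attack treated as merged, nominal visit days, a constant attack rate and a 183-day window. A reader might infer that the reported rates will be biased low. The documents do not support that, because most of the text points to Treatment Period 1 and the bias is then zero. What is established is an unresolved conflict in a rule that feeds both endpoints. The effect on the overall rate is small and matters mainly for subjects near a cut-off.

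**What to change.** In SAP 4.6, name Treatment Period 1 in the merged-attack sentence. State that attacks starting in the first two weeks of Treatment Period 2 and of the Extension are counted, apart from the rest-period and end-of-treatment exclusions already listed in 4.6.3. Numerator and denominator then cover the same days.

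If exclusion in every period was intended, keep the sentence, name the periods, and remove the same days from each length-of-stay formula in 4.6.3. The evaluation period and the time windows would need the same change.

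In either case, state that the same time window applies to the as-reported sensitivity analysis, so that it differs from the main analysis only in merging.

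The first option costs one changed phrase and one or two added sentences, with no new data. The attack-derivation program should be checked against the corrected text.
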